Clinical recovery is defined as all symptoms on the SARS-CoV-2 Infection Symptom Checklist 1 being recorded as 'absent' or 'mild' in intensity for at least 48 hours. To meet the clinical recovery, symptoms 'moderate' or 'severe' in intensity at baseline should be changed to 'mild' or 'absent', or symptoms 'mild' in intensity at baseline should be changed to 'absent', after the study drug administration. Symptoms "absent" in intensity at baseline should maintain as "absent" for at least 48 hours. If a symptom 'absent' in intensity at baseline becomes 'severe', 'moderate', or 'mild' during the study, this should be changed back to 'absent' for at least 48 hours. In Part 2, missing symptoms at baseline should become 'absent' for at least 48 hours.

The SARS-CoV-2 Infection Symptom Checklist 1 will be recorded once at Screening. On the date of study drug administration (Day 1), the checklist will be recorded once before

the study drug administration. If Screening visit date and the date of study drug administration are the same, the checklist will be also recorded once before the study drug administration. From Day 2 and up to Day 28, the checklist will be recorded once a day at approximately 24-hour interval in the evening (between 6 and 10 PM, approximately).

After Day 28, additional recording of the checklist will be required if following conditions are met:

- For patient who achieves the clinical recovery on Day 28 (or Day 27), the patient will record the checklist until Day 30 (or Day 29) to confirm whether the patient's condition is maintained at least 48 hours.
- For patient who shows deterioration (at the discretion of the investigator) or is still not recovered, the patient will record the checklist until the achievement of clinical recovery.
- For patient with suspicious ADE occurrence, the patient will record the whole patient diary for 7 days from the day of suspicious ADE occurrence (specified in [Table 11-3](#)). If suspicious ADE has not resolved or has worsened during the 7 days, same procedure of recording the whole patient diary for 7 days will be repeated from the beginning until the symptoms are resolved and/or no SARS-CoV-2 infection is confirmed by RT-PCR (local).

Body temperature will be collected in the SARS-CoV-2 Infection Symptom Checklist 1 for the patients who record feeling feverish as the baseline symptoms of SARS-CoV-2 infection at Screening, or for the patients who record feeling feverish at any time throughout the study.

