6.6.2 Sample Storage and Shipment

During the study, blood samples for PK, immunogenicity, virology and safety analyses will be collected.

Where appropriate, the serum should be transferred into a sufficient number of transfer tubes for transport to assigned testing facilities. Primary and backup samples will be shipped to the central laboratory according to the laboratory manual, and primary samples should be shipped separately from the backup samples.

Additionally, backup samples for PK and immunogenicity should be retained at the central laboratory as a backup for up to 5 years after the end of the study in case additional analysis is required. If additional analysis for PK and immunogenicity is not required, the sample will be stored at the sponsor or a designated biobank for a further 5 years (from the date the sample is transferred to the biobank) unless a specific authorization is given by the sponsor to destroy the sample. Additional tests can be conducted at the sponsor or the biobank if it is required from a regulatory or medical perspective. Details in storage and shipment will follow the laboratory manual. Virology samples will be secured at the central laboratory for analysis and backup samples will be retained. Additional tests can be conducted for virology samples with suspected resistance. The samples can be destroyed by a specific authorization of the sponsor.

7 Statistical Analysis Plan

The statistical analysis will be performed using Statistical Analysis System (SAS) software Version 9.4 or higher (SAS Institute, Inc., Cary, North Carolina, USA). The statistical methods for this study will be described in a detailed statistical analysis plan (SAP).

Changes from analyses planned in this protocol will be documented in the SAP. Any deviations from the planned analysis as described in the SAP will be justified and recorded in the CSR.

Randomization will be stratified by age (≥ 60 years vs. < 60 years), baseline comorbidities (Yes vs. No, having at least one of cardiovascular disease, chronic respiratory disease,

hypertension, diabetes mellitus, and pneumonia), region and participation in PK sub-study (Yes vs. No) in Part 1, and by age (≥ 60 years vs. < 60 years), baseline comorbidities (Yes vs. No, having at least one of cardiovascular disease, chronic respiratory disease, hypertension, diabetes mellitus, and pneumonia) and region in Part 2, respectively.

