 14. Patients will be instructed to complete the patient diary for SARS-CoV-2 Infection Symptom Checklist 1 once a day at approximately 24-hour interval in the evening (between 6 and 10 PM, approximately), and SARS-CoV-2 Infection Symptom Checklist 2 once a day in the evening (between 6 and 10 PM, approximately) from Day 1 until Day 28 (more details specified in [Section 6.1.1.1](#) and [6.1.1.2](#)). After Day 28, additional recording of the diary will be required if following conditions are met:
 - For patient who achieves clinical recovery on Day 28 (or Day 27), the patient will record the SARS-CoV-2 Infection Symptom Checklist 1 until Day 30 (or Day 29) to confirm whether the patient's condition is maintained at least 48 hours. For patient who shows deterioration (at the discretion of the investigator) or is still not recovered, the patient will record the SARS-CoV-2 Infection Symptom Checklist 1 until achievement of clinical recovery.
 - For patients with suspicious ADE occurrence, the patient will record the whole patient diary for 7 days from the day of suspicious ADE occurrence (specified in [Table 11-3](#)). If suspicious ADE has not resolved or has worsened during the 7 days, same procedure of recording the whole patient diary for 7 days will be repeated until the symptoms are resolved and/or no SARS-CoV-2 infection is confirmed by RT-PCR (local).
- Body temperature will be collected in the SARS-CoV-2 Infection Symptom Checklist 1 for the patients who record feeling feverish as the baseline symptoms of SARS-CoV-2 infection at Screening, or for the patients who record feeling feverish at any time throughout the study.
- However, if patient's condition is not available to record the diary at the discretion of investigator (e.g. sedation state for mechanical ventilator therapy), recording can be discontinued. Recording will be resumed when the patient's condition becomes available to record the patient diary.
15. SARS-CoV-2 infection related signs and symptoms should include, at a minimum, the examination of ear, nose, throat, sinuses, and lungs and the assessment for potential complications of SARS-CoV-2 infection throughout the study. During the Follow-up Period, patients will be asked if they have any SARS-CoV-2 infection related signs and symptoms by telephone calls.

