For time to event endpoints (the second and third key secondary endpoints), Kaplan-Meier methodology will be used to estimate the 25th percentile, 50th percentile (median) and 75th percentile in each treatment arm. The Brookmeyer-Crowley methodology (via log-log transformation) will be used to construct the 95% CI for each percentile. The treatment difference will be assessed by the stratified log-rank test presenting p-value. Hazard ratio between two treatment groups and associated 95% CI will be estimated using the stratified Cox proportional hazard model. Since clinical recovery is beneficial outcome, not hazard, the hazard ratio will be expressed as recovery rate ratio.

For time to clinical recovery endpoints, patients who report at least one symptom at baseline will be included in the analysis.

Clinical recovery is defined as all symptoms on the SARS-CoV-2 Infection Symptom Checklist 1 being recorded as 'absent' or 'mild' in intensity for both at least 48 hours. To meet the clinical recovery, all symptoms of SARS-CoV-2 Infection Symptom Checklist 1 defined in [Table 2](#) should satisfy one of the following conditions.

- ✓ Symptoms 'severe' or 'moderate' in intensity at baseline should be changed to 'mild' or 'absent' after the study drug administration for at least 48 hours.
- ✓ Symptoms 'mild' in intensity at baseline should be changed to 'absent' after the study drug administration for at least 48 hours.
- ✓ Symptoms 'absent' in intensity at baseline should maintain as 'absent' for at least 48 hours.
- ✓ Symptoms 'absent' in intensity at baseline becomes 'severe', 'moderate', or 'mild' during the study and changes back to 'absent' for at least 48 hours.
- ✓ Missing symptoms at baseline becomes 'absent' for at least 48 hours.

Patients who meet the clinical recovery criteria for at least two consecutive time points at each symptom will be considered as satisfying condition of 48 hours and achieving clinical

recovery at the first time point. The checklist at Screening or on Day 1 will be used to determine baseline and checklist from Day 2 will be used to determine clinical recovery. If the checklist from Day 2 is recorded twice a day, evening diary will be used to determine clinical recovery. From Day 2, missing time in SARS-CoV-2 Infection Symptom Checklist 1 will be imputed as 10PM for calculation of time to recovery.

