9.3. Other Secondary Efficacy Endpoints

The following secondary efficacy endpoints will be assessed up to Day 14 and up to Day 28, unless otherwise specified:

- Proportion of patients requiring supplemental oxygen due to SARS-CoV-2 infection (after study drug administration)
- Proportion of patients with intensive care unit transfer due to SARS-CoV-2 infection (after study drug administration)
- Proportion of patients with all-cause mortality (after study drug administration)
- Time to clinical recovery (after study drug administration)
- Duration of fever defined as the last day in the patient diary on which the temperature >38 °C (100.4 °F) is recorded, or a potentially antipyretic drug (acetaminophen or ibuprofen) is taken.
 - Duration of fever will be calculated for patients with the temperature >38 °C (100.4 °F) or a potentially antipyretic drug on or before study drug administration.
 - A potential antipyretic drug (including but not limited to acetaminophen, paracetamol or ibuprofen) will be identified by medical review.

- Proportion of patients with hospital admission due to SARS-CoV-2 infection (after study drug administration)
- Proportion of patients with mechanical ventilation due to SARS-CoV-2 infection (after study drug administration)
- Proportion of patients requiring rescue therapy due to SARS-CoV-2 infection (after study drug administration)
 - Rescue therapy is defined as prohibited therapy on or after the study drug administration on Day 1.
 - A prohibited therapy due to SARS-CoV-2 infection (including but not limited to remdesivir, chloroquine, hydroxychloroquine, dexamethasone [alternative corticosteroids to dexamethasone], interferon beta-1b, ribavirin, lopinavir-ritonavir, human intravenous immunoglobulin, convalescent plasma, tocilizumab, sarilumab, SARS-CoV-2 vaccine) will be identified by medical review before unblinding.
- Proportion of patient with negative conversion in nasopharyngeal swab specimen based on RT-qPCR at each visit (after study drug administration)
 - Patients who have negative result for at least two consecutive time points will be considered as satisfying negative conversion at the first time point. The two consecutive time points will be determined excluding missing data. If patients who have one negative result followed by all missing results will also be considered as satisfying negative conversion.

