9.4. Patient Diary

Patient diary consists of SARS-CoV-2 Infection Symptom Checklist 1 and 2. Patient diary will be issued to all patients at Screening and patients will be required to record the diary daily from Day 1 until Day 28, and after Day 28 if applicable (Protocol Section 6.1.1.1 and 6.1.1.2) after patients got instructed on how to appropriately complete the patient diary. Signs and symptoms of SARS-CoV-2 infection recorded in the patient diary throughout the study will not be reported as AEs.

9.4.1. SARS-CoV-2 Infection Symptom Checklist 1

SARS-CoV-2 Infection Symptom Checklist 1 consists of 7 symptoms and the intensity of patient's self-aware for each SARS-CoV-2 infection symptom. The 7 symptoms of SARS-CoV-2 infection are feeling feverish, cough, shortness of breath or difficulty breathing, sore throat, body pain or muscle pain, fatigue, and headache. Scores for SARS-CoV-2 infection symptom are absent (0), mild (1), moderate (2), and severe (3), defined as below [Table 2](#):

Table 2. SARS-CoV-2 Infection Symptom Checklist 1

	Intensity (score)	Absent (0)	Mild (1)	Moderate (2)	Severe (3)
1	Symptoms				
	Feeling feverish*				

2	Cough				
3	Shortness of breath or difficulty breathing				
4	Sore throat				
5	Body pain or muscle pain				
6	Fatigue				
7	Headache				

* If patient checks ‘Feeling feverish’ as Mild, Moderate, or Severe, body temperature will be recorded in the patient diary.

Mild: no interference with normal daily activity

Moderate: interferes with normal daily activity

Severe: prevents normal daily activity

The SARS-CoV-2 Infection Symptom Checklist 1 will be recorded once at Screening.

On the date of study drug administration (Day 1), the checklist will be recorded once; before the study drug administration. If Screening visit date and the date of study drug administration are the same, the checklist will be also recorded once; before the study drug administration. From Day 2 and up to Day 28, the checklist will be recorded once a day at approximately 24-hour intervals in the evening (between 6 and 10 PM, approximately).

After Day 28, additional recording of the checklist will be required if following conditions are met:

- For patient who achieves the clinical recovery on Day 28 (or Day 27), the patient will record the checklist until Day 30 (or Day 29) to confirm whether the patient’s condition is maintained at least 48 hours.

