11.1.3. Viral Serology for SARS-CoV-2 Antibody

Viral serology for SARS-CoV-2 antibody test with assays detecting serum antibodies against SARS-CoV-2 will be performed locally using the serum samples (if the assay is available). Viral serology for SARS-CoV-2 antibody result will be summarized on the ITTI Set by each treatment group at each scheduled visit using frequency table.

12. Changes in the Planned Analysis

- For patients who had negative result at Day 1 or missing Day 1 result of RT-qPCR, the ITTI Set will also include these patients if they are confirmed SARS-CoV-2 infection positive by Day 2 or Day 3. These patients can also be considered as infected since the virus was detected at Day 2 or Day 3.
- All expression or text regarding phenotype will be deleted in SAP since phenotype was not analyzed.

13. Reference List

International Council for Harmonisation (ICH) Assembly. ICH E9: Statistical principles for clinical trials – Step 5. 01 September 1998.

US Department of Health and Human Services. (2010). National Institutes of Health, National Cancer Institute. Common Terminology Criteria for Adverse Events (CTCAE) Version 5.0. Available from: <http://evs.nci.nih.gov/ftp1/CTCAE/About.html>.

Chan, I. S. F., and Zhang, Z. (1999). Test-Based Exact Confidence Intervals for the Difference of Two Binomial Proportions. Biometrics 55:1202–1209.

Schoenfeld, D. (1981). The asymptotic properties of nonparametric tests for comparing survival distributions. Biometrika. 68 (1): 316–319.

CDER, CBER, Multiple Endpoints in Clinical Trials. Guidance for Industry. Draft Guidance. January 2017. Available from: <https://www.fda.gov/files/drugs/published/Multiple-Endpoints-in-Clinical-Trials-Guidance-for-Industry.pdf>

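### SAP 9.2 accepts two once-daily evening diary entries, about 24 hours apart, as proof of recovery lasting at least 48 hours

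*SAP*

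**What the plan says.** Protocol 7.2 and SAP 9.2 require each Checklist 1 symptom to meet its recovery condition for at least 48 hours.

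On recording frequency, SAP 9.4.1 says that from Day 2 to Day 28 "the checklist will be recorded once a day at approximately 24-hour intervals in the evening (between 6 and 10 PM, approximately". Protocol 6.1.1.1 and Table 11-2, note 14, agree. SAP 9.2 reduces any denser diary to the same frequency: "If the checklist from Day 2 is recorded twice a day, evening diary will be used to determine clinical recovery".

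SAP 9.2 then turns the duration into a count. Patients that "meet the clinical recovery criteria for at least two consecutive time points at each symptom will be considered as satisfying condition of 48 hours" are recovered as of the first of those entries.

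For recovery at the end of the diary, on Day 28 (or Day 27), Table 11-2, note 14, says "the patient will record the SARS-CoV-2 Infection Symptom Checklist 1 until Day 30 (or Day 29) to confirm whether the patient's condition is maintained" for 48 hours or more. Protocol 6.1.1.1 and SAP 9.4.1 carry the same instruction.

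Protocol section 7 says: "Changes from analyses planned in this protocol will be documented in the SAP". SAP section 12 lists two changes. One begins "For patients who had negative result at Day 1 or missing Day 1 result of RT-qPCR, the ITTI Set will also include these patients"; the other removes phenotype.

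**The concern.** With one entry per evening, two consecutive entries on adjacent days are about 24 hours apart, so the rule does not demonstrate the duration in the endpoint's definition. A patient who qualifies on two evenings and is symptomatic again on the third counts as recovered, dated at the first evening. Patients who are still clear on the third evening are classified identically under either rule.

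The endpoints exposed are time to clinical recovery up to Day 14 in high-risk patients and in all randomized patients (the second and third key secondary endpoints, both in the fixed testing sequence) and the secondary time to clinical recovery. The primary endpoint and the first key secondary endpoint do not use the rule.

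A related gap is that SAP 9.2 does not say whether a missed evening breaks a consecutive run. For swabs, SAP 9.3 does: "The two consecutive time points will be determined excluding missing data".

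**Working it through.** **Diary span.** Inputs: one entry per day, window 6 to 10 PM (SAP 9.4.1; Protocol Table 11-2, note 14). For k entries on consecutive days, the span is 24 × (k − 1) hours, plus or minus 4 hours for the window.

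| Entries | Nominal span | Range |
|---|---|---|
| 2 | 24 h | 20–28 h |
| 3 | 48 h | 44–52 h |

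Two adjacent entries cannot reach 48 hours even at the edges of the window. Three is the smallest number that does so nominally.

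**The end-of-diary check.** Day 28 to Day 30 is 2 × 24 = 48 hours, and at one entry per day it gives three entries (28, 29, 30). Day 27 to Day 29 is the same. The Day 27 case is the more telling. Under a two-entry rule the Day 28 entry, already in the routine diary, would settle it, and there would be no reason to record to Day 29.

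**The plan's stated power.** Inputs from SAP 5.2: 1300 patients (822 high-risk), 90% symptomatic at baseline, 2-sided 5%, recovery ratio 1.5 with 66% recovering (high-risk) and 1.35 with 65% recovering (all randomized). By Schoenfeld with 1:1 allocation, power = Φ(√(E/4) × ln(ratio) − 1.96).

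- High-risk: E = 822 × 0.90 × 0.66 = 488; power 99.4%.
- All randomized: E = 1300 × 0.90 × 0.65 = 760.5; power 98.5%.

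Both satisfy the stated minimum of 90%. If a third entry removed 30% of events with the ratio unchanged, 342 and 532 events would remain and power would be 96.3% and 93.3%. Power of 90% needs 256 and 467 events, so the tolerable losses are 1 − 256/488 = 48% and 1 − 467/760.5 = 39%.

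**Effect on recovery counts.** The documents give neither a clearance nor a relapse rate, so everything here is assumed. The model has two states and moves daily. Patients are symptomatic at baseline and observed on evenings from Day 2. Recovery is dated at the first of two or three consecutive clear evenings and counted if dated by Day 14. Each scenario has 400,000 simulated patients. A two-entry recovery is unchanged if the patient does not relapse by the third evening, so the unchanged share is 1 minus the daily relapse probability. With 8% daily clearance:

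| Daily relapse | Unchanged | Lost by Day 14 | Dated later | Recovered by Day 14: two entries → three |
|---|---|---|---|---|
| 5% | 95% | 3.5% | 1.5% | 64.0% → 61.7% |
| 10% | 90% | 7.3% | 2.8% | 61.9% → 57.3% |
| 20% | 80% | 15.8% | 4.2% | 56.9% → 47.9% |

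Across clearance of 6% to 10% per day, the drop ranges from 2.1 to 9.6 percentage points.

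**Effect on the rate ratio.** Two arms of 1,000,000, with clearance 11.5% (active) and 8% (placebo) per day and a Mantel-Haenszel-type daily rate ratio:

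| Daily relapse, active / placebo | Two entries | Three entries |
|---|---|---|
| 10% / 10% | 1.43 | 1.42 |
| 5% / 10% | 1.52 | 1.60 |
| 10% / 5% | 1.35 | 1.26 |

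With identical arms the ratio is 1.00 under both rules.

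**The case against.** The protocol never says how many entries make 48 hours. It leaves detail to the SAP, and SAP 9.2 states its rule openly. On that view this is an operational definition rather than a departure that had to appear in section 12. That is fair as to disclosure: the rule is not hidden. It does not make a 24-hour span into 48 hours, and section 12 is silent.

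A better argument is that two daily ratings represent two days. Checklist 1's severity anchors refer to daily activity, and the reading is not excluded. But neither document states it. Checklist 2 has a 24-hour recall period and Checklist 1 has none. SAP 9.2 also treats Checklist 1 entries as points in time: a missing time is imputed as 10 PM, and time to recovery is calculated from date and time.

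The Day 28-to-30 text says how long to record, not how to derive the endpoint, and it also appears in the Part 1 schedule (Table 11-1, note 15) beside twice-daily recording. It therefore establishes a 48-hour calendar span, and the count of three comes from combining it with the Part 2 frequency. That combination is sound, because Table 11-2, note 14, and SAP 9.4.1 set the two side by side.

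Three further points stand. Three entries can span as little as 44 hours, so the stricter rule is closer to the definition but not exact. If a missed evening is skipped over, two recorded entries could be 48 hours apart, so the 24-hour figure applies to adjacent days. And both arms share the rule; with equal relapse the rate ratio hardly moves, and where active patients relapse less the two-entry rule understates the benefit.

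**Conclusion.** The concern holds. Two adjacent evening entries cover 20 to 28 hours, which is short of the stated 48, and the documents' own end-of-diary check points to three. This follows from the recording schedule and needs no outside assumption. It would fail only if each Checklist 1 entry were taken to cover a full day, which neither document says.

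The size is uncertain. On the assumed rates, recovery by Day 14 would be 2.1 to 9.6 percentage points lower under three entries. The rate ratio changes materially only if relapse differs between arms, and then in either direction, so no direction of bias can be claimed. The primary endpoint is unaffected. The point should be corrected because two tests in the fixed sequence rest on a duration that the rule does not show.

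**What to change.** Before unblinding, amend SAP 9.2 to require at least three consecutive daily evening entries (first to last about 48 hours; 44–52 hours within the diary window), dated at the first entry. State whether a missed evening breaks the run. Keep the two-entry version as a sensitivity analysis.

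If the two-entry rule is retained, describe the endpoint as two consecutive daily entries, about 24 hours apart; record this in SAP section 12; state the missed-evening rule; and add the three-entry version as a sensitivity analysis.

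Either route takes a small text edit and a derivation change, with no new data: the diary runs to Day 28, so a recovery dated Day 14 can be confirmed on Days 15 and 16. The price of three entries is somewhat fewer or later recoveries and more exposure to missed evenings, which the power margin can absorb.

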5.2 Treatment Administered

When calculating total volume of study drug to be administered, the body weight of each patient measured on Day 1 will be used.

In Part 1, CT-P59 80 mg/kg, 40 mg/kg, and placebo matching in volume of CT-P59 80 mg/kg will be administered as an IV infusion over 90 minutes (± 15 minutes). Patients with body weight at or above 100 kg and who are allocated to CT-P59 80 mg/kg group or placebo group will receive 8,000 mg of CT-P59 or matching volume of placebo.

In Part 2, based on the result from Part 1, CT-P59 40 mg/kg and placebo matching in volume of CT-P59 40 mg/kg will be administered as an IV infusion over 60 minutes (± 15 minutes). Patients with body weight at or above 200 kg will receive 8,000 mg of CT-P59 or matching volume of placebo.

All patients in both Part 1 and Part 2 will be given optimal SoC. Optimal SoC can include rehydration therapy, antipyretics or antitussives prescribed by the investigator's discretion. Potential antiviral drugs and/or possible anti-SARS-CoV-2 activity drugs are not allowed during the study, unless specified in [Section 5.7](#). The routine use of antibiotics is not recommended, but antibiotics may be used if bacterial infections are present or suspected. The type of antibiotic will be selected based on the patient's clinical disease status and symptoms with discretion of investigator.

A 250 mL infusion solution of 0.9% weight/volume sodium chloride will be used for patient infusion. The bag will be gently inverted to mix the solution in order to avoid foaming. Parenteral solutions will be inspected visually for particulates and discoloration prior to administration and administration will not be performed if any particulates and discoloration are found. The detailed method about mixing the solution will be described in the pharmacy manual.

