9.1. Primary Efficacy Analysis

The primary efficacy endpoint of Part 2 is proportion of patients with clinical symptom requiring hospitalization, oxygen therapy, or experiencing mortality due to SARS-CoV-2 infection up to Day 28 in high-risk patients.

Patients who have hospitalization record (≥ 24 hours of acute care) in “Disease Status Monitoring” page of eCRF and received treatment such as oxygen therapy due to SARS-CoV-2 infection (as defined in this section), remdesivir or tocilizumab (from “Prior & Concomitant Medications” page of eCRF) during period of the hospitalization will be considered to have required hospitalization due to SARS-CoV-2 infection. If the start date and stop date are the same in “Disease Status Monitoring” page of eCRF, the duration of hospitalization is considered as < 24 hours. List of treatment will be determined by medical review before unblinding.

Patients who have supplemental oxygen record (at least 24 hours) in “Disease Status Monitoring” page of eCRF and SpO₂ measure in room air shows $\leq 94\%$ before applying supplemental oxygen will be considered to have required oxygen therapy due to SARS-CoV-2 infection. If the start date and stop date are the same in “Disease Status Monitoring” page of eCRF, the duration of supplemental oxygen is considered as < 24 hours. The SpO₂ measure of $\leq 94\%$ in room air will be confirmed based on “Vital Signs” page of eCRF on the starting day of supplemental oxygen. If there is no record of SpO₂ on the starting day of supplemental oxygen in the “Vital Signs” page of eCRF or the SpO₂ does not meet $\leq 94\%$ in room air, the SpO₂ will be identified based on description on “Disease Status Monitoring” page of eCRF.

Patients whose ‘Reason for End of Treatment Period’ on “End of Treatment Period” page of eCRF or ‘Reason for End of Follow-Up Period’ on “End of Follow-Up Period” page of eCRF is recorded as death and the cause of death is SARS-CoV-2 infection will be considered as experiencing mortality due to SARS-CoV-2 infection. The cause of death will be confirmed through “General Comments” page of eCRF or ‘If death, Reason of Death’ on End of Follow-Up Period” page of eCRF.

Proportion of patients with clinical symptom requiring hospitalization, oxygen therapy, or experiencing mortality due to SARS-CoV-2 infection up to Day 28 in high-risk patients will be presented along with 95% Wilson (score) CI for the proportion in each treatment

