Time to clinical recovery is defined as the elapsed time (in days) from the study drug administration to the earliest day satisfying condition for clinical recovery, and calculated as (Date/time of event or censoring – Date/time of study drug administration). The following patients will be considered censored at their scheduled visit of interest (Day 14).

- Patients who are ongoing in the study without event
- Patients with death or early withdrawal for any reason prior to their scheduled visit of interest (Day 14)
- Patients who administered the rescue therapy due to SARS Cov-2 infection (as defined in [Section 9.3](#)) prior to their scheduled visit of interest (Day 14)
- Patients who were hospitalized due to SARS-CoV-2 infection (as defined in [Section 9.1](#)) prior to their scheduled visit of interest (Day 14)

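### Clinical recovery is censored for rescue therapy and hospitalization but not for qualifying oxygen, so a patient on oxygen outside a qualifying hospital stay can be scored as recovered

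*SAP*

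**What the plan says.** **Recovery.** SAP 9.2 rests recovery on the symptom diary alone: "Clinical recovery is defined as all symptoms on the SARS-CoV-2 Infection Symptom Checklist 1 being recorded as 'absent' or 'mild' in intensity", with further conditions that depend on the baseline intensity. A symptom that was moderate or severe at baseline qualifies once it is mild or absent; one that was mild, absent or missing must be absent. Two consecutive diary time points satisfy the 48-hour condition, and recovery is dated to the first. Neither oxygen nor medication enters the definition.

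**Censoring.** SAP 9.2 then names four groups censored at Day 14: patients without an event, those who died or withdrew early, "Patients who administered the rescue therapy due to SARS Cov-2 infection", and "Patients who were hospitalized due to SARS-CoV-2 infection". The hospitalization bullet refers back to SAP 9.1.

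**Primary components.** SAP 9.1 defines hospitalization and oxygen separately. Hospitalization starts from "Patients who have hospitalization record (≥ 24 hours of acute care) in" the disease status page and also requires treatment such as qualifying oxygen, remdesivir or tocilizumab during the stay. Patients with at least 24 hours of supplemental oxygen and a preceding room-air SpO2 of 94% or below "will be considered to have required oxygen therapy due to SARS-CoV-2 infection"; no hospital record is asked for.

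**Rescue and setting.** Rescue therapy is prohibited therapy (SAP 9.3) or prohibited medication (Protocol 6.1.2.5). Neither that list nor Protocol 5.7 names oxygen. Outpatients may be in home quarantine or confined at the study center (SAP 4.1).

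**The concern.** The censoring list takes up two of the plan's markers of deterioration and leaves out a third, without giving a reason. Someone given qualifying oxygen in home quarantine, with no rescue drug, stays eligible for recovery. If breathlessness was moderate or severe at baseline, a rating of mild while on oxygen is enough for that symptom. If the other six symptoms also qualify at two consecutive time points, the patient is recovered in time to clinical recovery and a failure in the composite.

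Time to clinical recovery supplies the second and third of the three key secondary tests in the fixed sequence, so its event definition should be free of such gaps. If CT-P59 works as planned, oxygen need is concentrated on placebo, and the gap then credits placebo with recoveries it should not have.

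**Working it through.** **1. Can the case occur as the plan is written?**

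| Situation before Day 14 | Primary event (SAP 9.1)? | Barred from recovery (SAP 9.2)? |
|---|---|---|
| Hospital stay of at least 24 h with qualifying oxygen | Yes | Yes, hospitalization |
| Qualifying oxygen plus a rescue drug, any setting | Yes | Yes, rescue therapy |
| Qualifying oxygen, no qualifying stay, no rescue drug | Yes | No |

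Only the third row is open. As a cross-check, breathing oxygen scores 2 on NEWS2 (SAP Appendix 4), so the same patient cannot reach NEWS2 of 0 while on oxygen.

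**2. The plan's own recovery power (SAP 5.2).** Events = N × 0.90 × share recovering. Schoenfeld power = Φ(½√events × ln ratio − 1.96), for 1:1 allocation and two-sided 5%.

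- High-risk: 822 × 0.90 × 0.66 = 488 events; ½ × √488 × ln 1.5 = 4.48; 4.48 − 1.96 = 2.52; power 99.4%.
- All randomized: 1300 × 0.90 × 0.65 = 760 events; ½ × √760 × ln 1.35 = 4.14; 4.14 − 1.96 = 2.18; power 98.5%.

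Both reproduce the stated figure of at least 90%.

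**3. Ceiling on the number affected.** Planned composite events up to Day 28:

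- High-risk: 411 × 0.071 = 29.2 placebo and 411 × 0.029 = 11.9 CT-P59, total 41.1; placebo share 29.2/41.1 = 71%.
- All randomized: 650 × 0.055 = 35.8 and 650 × 0.025 = 16.3, total 52.0; placebo share 69%.

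These counts include every hospitalization and death, and events after Day 14, so they bound the affected group from above. The documents do not split the composite, so the share affected, f, is an assumption.

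**4. Dilution.** Assume proportional hazards and take the Day 14 recovered proportions that average to the planned share. High-risk: 0.586 placebo and 0.734 CT-P59, since ln(1 − 0.734)/ln(1 − 0.586) = 1.50 (unrounded proportions used). All randomized: 0.595 and 0.705. Add f times the composite rate to each arm as false recoveries, and recompute the ratio as ln(1 − CT-P59)/ln(1 − placebo). For f = 10% in high-risk patients, placebo becomes 0.586 + 0.0071 = 0.593, CT-P59 becomes 0.734 + 0.0029 = 0.737, and the ratio is 1.483. Power at the apparent ratio uses the step 2 formula with the planned event count.

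| f | High-risk ratio | Power | All randomized ratio | Power |
|---|---|---|---|---|
| 0 | 1.50 | 99.4% | 1.35 | 98.5% |
| 10% | 1.48 | 99.2% | 1.34 | 98.1% |
| 25% | 1.46 | 98.7% | 1.32 | 97.1% |
| 100% | 1.34 | 90.4% | 1.25 | 86.0% |

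The last row is a limit and not a scenario. It would need every composite event to be oxygen without a qualifying stay or rescue drug, before Day 14, and scored as recovered.

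**5. What the fix could cost in events.** Removing 0.90 × f × total composite events at the planned ratio takes out 4 (f = 10%) to 37 (f = 100%) of 488 high-risk recoveries, with power 99.4% to 99.1%. For all randomized patients it takes out 5 to 47 of 760, with power 98.5% to 98.0%.

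**The case against.** The best defence is that the open route is narrow. Oxygen during a hospital stay of at least 24 hours is already censored. Protocol 6.1.2.4 records hospitalization for oxygen therapy or acute care in a hospital or similar facility, so some study-center confinement may be captured too. The rescue list is open-ended and settled by medical review, and many patients who need oxygen would also receive a listed drug. All of this stands. It limits how often the gap is used but does not close it.

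The two endpoints may also legitimately disagree. The composite is ever-by-Day-28, while recovery is the first qualifying day up to Day 14. A patient may recover on Day 6 and need oxygen on Day 20, or need oxygen on Day 3 and truly recover by Day 12. That stands as well: being both a failure and recovered is not in itself an error. The problem is that the plan bars the second patient from recovery if the oxygen was given in hospital and not if it was given at home.

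A reader might go further and infer that permitted symptom relief undermines recovery in the same way. Protocol 5.2 allows "rehydration therapy, antipyretics or antitussives", and duration of fever in SAP 9.3 runs to the last day with fever "or a potentially antipyretic drug (acetaminophen or ibuprofen) is taken", whereas recovery ignores such use. The documents do not support treating this as a defect. Background care is open to both blinded arms and is part of the comparison. Fever duration and self-rated intensity are different constructs, and no endpoint takes antitussive use into account. The diary checklists have no medication field, so drug-free days would rest on start and stop dates, with a missing stop day imputed to month-end (SAP 8.1). A sensitivity analysis on this is optional.

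**Conclusion.** The point holds as a gap in the SAP 9.2 censoring list, limited to qualifying oxygen outside a qualifying hospitalization and without a rescue drug. It is minor. At the planned rates the affected patients would be mostly on placebo (about 71% of composite events in high-risk patients), and the recovery ratio would move from 1.50 to about 1.48 if 10% of events were affected, with power falling from 99.4% to 99.2%. These figures rest on the planned event rates, on an assumed affected share that the documents do not give, and on a simplified proportional-hazards model.

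Three stronger inferences should be resisted. It is not true that any patient on oxygen can be scored as recovered, because in-hospital oxygen of at least 24 hours is caught. Taking, say, 10% to 30% of the 41 high-risk events (4 to 12 patients) as a count of misclassified patients is not justified. Each would also need a baseline symptom, oxygen before Day 14, no rescue drug, and all seven symptoms qualifying at two consecutive time points. And the gap does not favour CT-P59: at the planned effect it pulls the ratio toward 1.

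**What to change.** Add one bullet to the SAP 9.2 censoring list, in the same form as the hospitalization bullet, for patients who met the SAP 9.1 oxygen definition before their scheduled Day 14 visit, and censor them at Day 14 in the same way. Do not attach a condition such as oxygen before recovery to this bullet alone, since the hospitalization bullet has none.

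State once, for rescue therapy, hospitalization and oxygen together, whether a recovery reached before the event still counts. The SAP does not say this for any of them at present. SAP 9.3 applies the same censoring rules to the other time-to-event endpoints, so say whether the oxygen rule is meant to carry over to them. Settle all of this before unblinding, as the SAP already does for its treatment lists.

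The cost is a few lines of text and programming. Start and end dates of oxygen are already collected (Protocol 6.1.2.1), and clinical care is unchanged. The downside is that a few patients who recover after a short oxygen course will no longer count as recovered, as already applies to hospitalized patients.
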